- An 18 gauge intravenous catheter will be inserted in order to draw blood.
- The participants will fast from 7 pm until after the next morning's testing.
- In the morning, while still supine after the overnight sleep, heart rate (HR) and blood pressure (BP) will be recorded, and blood will be drawn. The participants will then stand for 10 minutes. HR and BP will be measured at intervals, and an upright blood sample will be collected.
- The participants will be asked to collect their urine at the end of the 24hr urine collection. Another 24hr urine collection will then be started.

- Treatment A (carbidopa or placebo) will be given orally following the void, at approximately 7 am. Additional doses will be taken every 6 hours with the last dose at 7 am the following morning.
- Participants will remain inpatients on the CRC during the day. They will need to consume the 200 mEq sodium/day study diet for each meal, collect all urine, and take study medication on schedule. Supine BP and HR will be measured and blood will be collected for plasma carbidopa 2hr after each dose.
- The participants will fast after midnight except for water and medication.
- In the morning, supine and standing HR and BP will be recorded, and the participants will be asked to collect their urine to end the 24hr urine collection.
- The final dose of study medication (carbidopa or placebo) will be given orally following the void, at approximately 7 am.
- Supine HR and BP will be measured and supine blood samples will be collected hourly for 4 hours after the last dose and at 8 hours after the dose. Participants must rest supine for at least 30 minutes before each blood draw. Plasma carbidopa will be measured at 2hr, 4hr and 8hr after the 5th dose. The intravenous catheter will be removed following the 8-hour blood draw.
- At 2 hours after the 5th dose, participants will stand for 10 minutes for upright BP and HR measurements and collection of an upright blood sample, as described above. Participants will be asked to rate the severity of common orthostatic symptoms while supine and upright.
- As part of the safety assessment, the 12-lead ECG, CBC and chemistry panel will be repeated 2hr after the fifth dose.
- Urine will be collected for two 4-hour periods after the 5th dose followed by a 16-hour collection to finish the 24-hour cycle
- Participants may be discharged approximately 8 hours after the last dose or, if they prefer, they may remain on the CRC for the washout day.

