The history will include (but not be limited to):

- Framingham risk factors (age, gender, smoking, hypertension, dyslipidemia)
- Metabolic diseases (metabolic syndrome, polycystic ovary syndrome, diabetes)
- Inflammatory diseases (e.g., rheumatoid arthritis)
- Review of medication
- Date that last menstrual period started (if female).

The physical examination will include (at minimum):

- Height
- Weight
- Orthostatic vital signs (HR and BP)
- EKG
- Complete blood count
- Metabolic panel

4.D Retention Strategies

Follow-up. Study participation will be complete following the inpatient evaluation. There will be no further study follow-up.

Record retention. Study records will be kept for at least 7 years following the publication or presentation of the data collected as part of this study.

4.E Data Elements-Dose Escalation Study

- A dose escalation study will be conducted prior to the main study. A cohort consisting of one healthy volunteer and one patient with POTS will be administered a dose of 50mg carbidopa every 6 hours for a total of five doses. If this dose is well tolerated, a second cohort will be given five doses of carbidopa 100mg with 6 hours between doses. If this dose is well tolerated, a final cohort will take the proposed dose of 200mg carbidopa every 6 hours for five doses. A minimum of 9 days is needed to complete the study with 2 nights on the CRC for the active compound and 2 nights for the placebo.
- Pre-study assessments consist of 1) 12-lead ECG; 2) complete blood count (CBC:WBC, Hgb, PCV, Plt-Ct, RBC, MCV, MCH, MCHC, RDWSD, RDW, Neut, Lym, Monocy, Eos, Baso) with platelets; 3) chemistry panel (CMP: Na, K, Cl, CO₂, BUN, Creat, Gluc, Ca, Tprot) including albumin, total bilirubin, alkaline phosphatase, serum glutamic oxaloacetic transaminase (SGOT), and serum glutamic pyruvic transaminase (SGPT) to evaluate liver function; and 4) plasma carbidopa.
- Participants will be provided a 200 mEq/day sodium diet, free of methylxanthines and low in monoamines, by the kitchen of the Clinical Research Center (CRC).
- After achieving sodium balance on the study diet over 2-3 days, participants will collect urine over 24hr, starting at 0700hr, for baseline assessment of sodium, potassium and catecholamines and to confirm adherence to the study diet.
- Participants will be admitted to the CRC that afternoon or evening.

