- In the morning, while still supine and NPO after the overnight sleep, HR and BP will be recorded with a Dinamap electrocardiographic and BP (brachial cuff) recorder, and blood will be drawn for a basic metabolic panel, fractionated catecholamines, aldosterone and plasma renin activity. The participants will then stand for 10 minutes or for as long as they are able to tolerate. They may sit for short intervals if necessary. HR and BP will be measured at 1, 3, 5, and 10 minutes of standing, and an upright blood sample will be collected at 10 minutes for catecholamines, plasma renin activity, and aldosterone.
- The participants will be asked to void while recumbent, if able, or after the upright measurements, to end the first 24hr urine collection. Another 24hr urine collection will then be started for analysis of sodium, potassium and creatinine.
- Treatment A (carbidopa or placebo) will be given orally following the void, at approximately 0700hr. Additional doses will be taken every 6 hours with the last dose at 0700hr the following morning. BP and HR will be measured and plasma carbidopa will be measured 2 hours after each dose. Participants will remain on the CRC for monitoring.
- In the next morning, supine and standing HR and BP will be recorded with a Dinamap recorder, and the participants will be asked to void and collect the urine to end the 2nd 24hr urine collection.
- The final dose of study medication (carbidopa or placebo) will be given orally following the void, at approximately 0700hr.
- Supine HR and BP will be measured by Dinamap and supine blood samples will be collected hourly for 4 hours after the 5th dose and at 8 hours after the treatment. Participants must rest supine for at least 30 minutes before each blood draw. These samples will be analyzed for catecholamines (all samples), and plasma renin activity and aldosterone (only at 2 hr after treatment). In addition, a basic metabolic panel will be run for the 4-hour and 8-hour samples.
- Plasma carbidopa will be measured at 2hr, 4hr and 8hr after the final dose.
- As part of the dose escalation assessment, the 12-lead ECG, CBC and Comprehensive Metabolic Panel will be repeated 2hr after the 5th dose.
- At 2 hours after the 5th dose, participants will stand for 10 minutes for upright BP and HR measurements and collection of an upright blood sample, as described above. Participants will be asked to rate the severity of common orthostatic symptoms while supine and upright.

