- Urine will be collected for two 4-hour periods after the last dose followed by a 16-hour collection to finish the 24-hour cycle for analysis of sodium, potassium, catecholamines, and creatinine.
- Participants may be discharged from the CRC approximately 8 hours after the last dose.
- After at least 24 hours, the protocol will be repeated with treatment B (carbidopa or placebo, whichever was not administered during treatment A). Depending on the interval, participants will either remain on the study diet or re-start the diet 2-3 days before admission for the 2nd phase.
- Throughout the dosing period, participants will be monitored (HR and BP measurement, Psychiatric Symptom Questionnaire, and questioning by study personnel 2hr after each dose) for adverse events,

including allergic reaction, nausea, acute psychosis, worsening hypotension or tachycardia, arrhythmia, neuroleptic malignant syndrome, hallucinations or other psychiatric symptoms.

4.F Schedule of Events-Dose Escalation Study

Table 1 Study Schedule-Dose Escalation

Dosing Regimen	Time of Dose	Monitoring/Labs
Predose	NA	24hr urine for catecholamines, sodium, potassium, creatinine to start 24hr prior to 1 st dose; 12-lead ECG; CBC with platelets; chemistry panel including liver enzymes; supine and upright BP and HR; supine and upright plasma catecholamines, serum aldosterone, plasma renin activity; plasma carbidopa; metabolic panel; start a 2 nd 24hr urine for catecholamines, sodium, potassium, creatinine
Dose #1	0700	0900: supine BP and HR; Psychiatric Symptom Questionnaire; monitoring; plasma carbidopa
Dose #2	1300	1500: supine BP and HR; Psychiatric Symptom Questionnaire; monitoring; plasma carbidopa
Dose #3	1900	2100: supine BP and HR; Psychiatric Symptom Questionnaire; monitoring; plasma carbidopa
Dose #4	0100	0300: supine BP and HR; Psychiatric Symptom Questionnaire; monitoring; plasma carbidopa
Pre-Dose #5	0645	Supine and upright BP and HR; finish 24hr urine and start 4hr urine for catecholamines, sodium, potassium, creatinine
Dose #5	0700	0800: supine BP and HR; plasma catecholamines
		0900: supine and upright BP and HR; 12-lead ECG; CBC with platelets; chemistry panel including liver enzymes; Psychiatric Symptom Questionnaire; Orthostatic Symptom Questionnaire; monitoring; plasma carbidopa; supine and upright plasma catecholamines, serum aldosterone, plasma renin activity
		1000: supine BP and HR; plasma catecholamines

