		1100: supine BP and HR; metabolic panel; plasma catecholamines; plasma carbidopa; restart 4hr urine for catecholamines, sodium, potassium, creatinine
		1500: supine BP and HR; metabolic panel; plasma catecholamines; plasma carbidopa; start 16hr urine for catecholamines, sodium, potassium, creatinine

Table 2. Study Day Description-Dose Escalation

3

Day	Treatment	Time	Assessments for Tolerability	Obtain Consent	History & Physical	Pregnancy Test	Study Diet	Carbidopa or Placebo	Blood Draw	HR/BP	Urine
Pre-Study			X	X	X	X			X		
-3, -2						X					Start study diet
-1	0700					X					Start 24hr urine #1
1	0645					X			X	X	End & restart 24hr urine
	A 0700, 1300, 1900					X	Doses 1, 2, 3				Continue 24hr urine #2
	0900, 1500, 2100	X				X			X	X	Continue 24hr urine #2
2	0100					X	Dose 4				Continue 24hr urine #2
	0300	X				X			X	X	Continue 24hr urine #2
	0645-0700					X	Dose 5		X		End 24hr, start 4hr urine #1
	0800					X			X	X	Continue 4hr urine #1
	0900	X				X			X	X	Continue 4hr urine #1
	1000					X			X	X	Continue 4hr urine #1
	1100					X			X	X	End 4hr urine #1 & start 4hr urine #2
May be discharged	1500					X			X	X	End 4hr urine #2 & start 16hr
3(washout day)	0700					X					End 16hr urine
4	0700					X					Start 24hr urine
5	0645					X			X	X	End & restart 24hr urine
	B 0700, 1300, 1900					X	Doses 1, 2, 3				Continue 24hr urine #2
	0900, 1500, 2100	X				X			X	X	Continue 24hr urine #2
6	0100					X	Dose 4				Continue 24hr urine #2
	0300	X				X			X	X	Continue 24hr urine #2
	0645-0700					X	Dose 5		X		End 24hr, start 4hr urine #1
	0800					X			X	X	Continue 4hr urine #1
	0900	X				X			X	X	Continue 4hr urine #1
	1000					X			X	X	Continue 4hr urine #1
	1100					X			X	X	End 4hr urine #1 & start 4hr urine #2
	1500					X			X	X	End 4hr urine #2 & start 16hr
7	0700										End 16hr urine

4.G Data Elements-Main Study

- A minimum of 9 days is needed to complete the study with 2 nights on the CRC for the active compound and 2 nights for the placebo.
- Participants will be provided a 200 mEq/day sodium diet, free of methylxanthines and low in monoamines, by the kitchen of the Clinical Research Center (CRC).
- After achieving sodium balance on the study diet over 2-3 days, participants will collect urine over 24hr starting at 0700hr, for baseline assessment of sodium, potassium and catecholamines and to confirm adherence to the study diet.
- Participants will be admitted to the CRC that afternoon or evening.

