Sample Size Calculation. Based on our preliminary findings of a standard deviation for urinary sodium excretion of 30 mEq/g creatinine, a sample size of 16/group (32 total) will have 80% power to detect a difference in group means (control vs. POTS) of 31 mEq/g creatinine with a 0.05 two-sided significance level. To allow for participant drop-out prior to study completion, we will plan to obtain informed consent from 35 participants in total (18 POTS, 17 healthy controls).

Randomization procedures were performed by [REDACTED] and the results provided to Vanderbilt's Investigational Pharmacy. Prior to admission, the pharmacy is notified whether the participant is a patient or healthy volunteer and the Investigational Pharmacist determines the treatment order (placebo or carbidopa first). At the end of the study, the blinding will be broken by the Vanderbilt Investigational Pharmacy and the order of agents will be revealed to the investigators and to the participants, if they so request.

7. Data Management

The investigators, research personnel and nursing staff at the CRC will collect the majority of the data at the bedside in real time. Data will be handwritten on CRFs provided by [name]. Routine labs are sent to

the hospital laboratory for analysis. Special study specific labs (ex: catecholamines) are sent to the GCRC Core Lab for analysis. Laboratory data will be obtained from Vanderbilt Medical Center's online medical chart system (StarPanel) and from the GCRC Core Laboratory website, both of which are password protected and only authorized personnel have access. After all data points have been retrieved, a member of the research team will enter the data into the DMCC database, which is also password protected and only accessible to authorized personnel. Data analysis will be performed routinely for periodic review. Hard copies of the CRFs will be maintained in the patient's research chart in a locked cabinet. Study participation will be complete following the inpatient evaluation. There will be no further study follow-up. Study records will be kept for at least 7 years following the publication or presentation of the data collected as part of this study.

All study data will be collected via systems created in collaboration with the RDCRN Data Management and Coordinating Center and will comply with all applicable guidelines regarding patient confidentiality and data integrity.

7.A Registration

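### Dose escalation: scheduled symptom questioning ends 2 h after dose 5 in each period, with none before discharge at about 8 h or afterwards

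*Combined protocol and SAP*

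**What the plan says.** Sections 1.B and 4.E define adverse-event monitoring over the dosing period, including "questioning by study personnel 2hr after each dose". Table 1 (Section 4.F) carries this out at 0900, 1500, 2100 and 0300 for doses 1 to 4, and at 0900 for dose 5, which is given at 0700. The 0900 row after dose 5 is the last to list the Psychiatric Symptom Questionnaire or a monitoring entry. The tolerability column of Table 2 agrees: its last marks are 0900 on Day 2 and 0900 on Day 6, with none on Days 3, 4 or 7.

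Other observation continues. Section 4.E says that "supine blood samples will be collected hourly for 4 hours after the 5th dose and at 8 hours after the treatment", with supine vital signs at the same times. Table 1 adds metabolic panels at 1100 and 1500. Then "Participants may be discharged from the CRC approximately 8 hours after the last dose". Section 1.B adds that, "if they prefer, they may remain on the CRC for the washout day". The final urine collection closes at 0700 on Days 3 and 7, where Table 2 lists only "End 16hr urine".

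Follow-up is excluded in Section 4.D ("Study participation will be complete following the inpatient evaluation. There will be no further study follow-up") and again in Section 7 ("There will be no further study follow-up. Study records will be kept for at least 7 years").

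**The concern.** Tolerability is the first aim of the escalation study, and Section 5.C acknowledges that carbidopa has not been given before at this dose and interval. The events being watched for include nausea, hallucinations and other psychiatric symptoms. These are found mainly by asking; a blood pressure reading or metabolic panel will not show them. Plasma carbidopa is drawn at 4 h and 8 h after dose 5, yet no one is scheduled to ask how the participant feels at those times.

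Each cohort has two people. Under Section 1.B the medical monitor decides on the next dose by clinical judgment, with a general guide: grade 2 events in more than one participant, or one drug-related grade 3 event, lead to termination. With numbers this small, one event that nobody asked about could change whether the guide is met. At the 200 mg level the decision affected is whether the main study opens.

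**Working it through.** The plan gives no figure to reproduce here, so the check is clock arithmetic on Tables 1 and 2.

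**Unasked window after dose 5 (0700)**
- Last question at 0900: 2 h after the dose.
- Earliest discharge at about 1500: 8 h.
- End of the 16 h urine collection at 0700 next day: 24 h.
- No planned question: 24 − 2 = 22 h, made up of 8 − 2 = 6 h on the unit and 24 − 8 = 16 h after permitted discharge.

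**Doses 1 to 4 compared with dose 5**
- Counting from dose 1, doses fall at 0, 6, 12, 18 and 24 h and questions at 2, 8, 14, 20 and 26 h.
- Each of doses 1 to 4 therefore also has a question 8 h after it (2 h after the next dose). Dose 5 does not.
- That later question covers the preceding interval only if it looks back. The documents state no recall period.

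**Treatment order, on the minimum schedule of Table 2**
- Carbidopa first: dose 5 at 0700 on Day 2. The next question is at 0900 on Day 5, 74 h later, and the last is at 0900 on Day 6, 98 h later. There are five question times, all during placebo.
- Carbidopa second: no later question.
- The washout is a minimum of one day, so 74 h is the earliest time. At the half-life of about 2 h given in Section 3, 74 / 2 = 37 half-lives.

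**How much exposure lies in the gap**

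Assume immediate absorption and first-order elimination with a 2 h half-life, so the fraction remaining at time t is 2^(−t/2).
- At 2 h: 2^(−1) = 50%.
- At 8 h: 2^(−4) = 6.25%.
- At 24 h: 2^(−12) = 0.024%.
- Accumulation by dose 5 at 6 h dosing: r = 2^(−3) = 0.125, and (1 − r^5)/(1 − r) = 1.143. The level after dose 5 is about 14% above that after dose 1.
- Exposure remaining after any time is proportional to the level at that time. The share of post-0900 exposure that falls between 2 h and 8 h is (50 − 6.25)/50 = 87.5%. Slower absorption would lower this share.

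On these assumptions, one question at 1500 covers most of the exposure that now follows the last question.

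**Does another section fill the gap?**
- Section 5 makes the research team responsible for identifying adverse events and says monitoring is ongoing, but it schedules no contact.
- Section 5.G provides a final visit and clinical follow-up, under participant discontinuation. It does not cover those who complete.
- Staying on the unit (Section 1.B) is optional, and no questioning is attached to it.

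**The case against.** A reader might infer that treatment order is the real problem: carbidopa-first participants get follow-up in period B and carbidopa-second participants do not, so what the monitor sees depends on randomisation. The difference in schedule is real, but the documents do not support giving it that weight. Both orders share the same 22 h without a question. The later questions for carbidopa-first participants come at least 74 h after their last carbidopa dose, while they take placebo, and no recall period is stated. They are of little value for detecting carbidopa effects. Nor is it shown that review comes before any late information could arrive, because the protocol gives no date for it.

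A reader might also infer that participants are unobserved after 2 h. They are not. They remain on the unit to about 8 h, with vital signs, blood draws and metabolic panels, and volunteered reports are recorded.

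The strongest remaining argument concerns size. With a half-life of about 2 h, little drug is left at 8 h and almost none at 24 h, and accumulation by dose 5 is slight. If questions look back, the 2 to 8 h window has already been sampled four times per participant at similar exposure. This stands. It makes the 24 h contact secondary and keeps the expected benefit modest. It does not remove the case for a question at 1500, when about half the drug level present after dose 5 has yet to clear at the time of the last question.

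Two limits on the evidence also stand. The no-follow-up statement in Section 4.D is general and sits under retention, not in the safety plan. The escalation consent forms (Appendices 1c and 1d) were not available and may give post-discharge instructions. Neither affects the on-unit gap, which can be read directly from Table 1.

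**Conclusion.** The point holds as a statement about scheduled active questioning. In each period, and in both orders, it ends 2 h after dose 5, leaving 6 h on the unit and a further 16 h to the end of urine collection without a planned question. This is a stated schedule, not missing detail.

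The timings rest on Tables 1 and 2 as printed. The exposure shares rest on the 2 h half-life with immediate absorption and first-order elimination. The effect on safety findings cannot be sized, because no late-event rate is given, and it may be zero. The matter concerns six participants (3 cohorts × 2) and does not touch the main-study primary outcome. The change should be made because it is cheap and the regimen is new, but the gap does not undermine the study.

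**What to change.** **Main change.** At the existing 1500 draw, before discharge, repeat the adverse-event question, worded to cover the time since the last question, and the Psychiatric Symptom Questionnaire. Do this in both periods, so that carbidopa and placebo are assessed alike and the blind is kept.

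**Secondary change.** Add one brief adverse-event contact, by telephone or in person, at about 24 h, when the 16 h urine collection ends (0700 on Days 3 and 7). Amend Section 4.D and Section 7 to allow it. State in Section 1.B that the cohort summary goes to the medical monitor after the Day 7 contact.

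**Cost.** 6 participants × 2 periods = 12 questionnaires of a few minutes and 12 short contacts. Cohort review would wait up to 16 h (1500 on Day 6 to 0700 on Day 7). Dosing, sample size and analysis are unchanged.

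**What it leaves open.** Events arising after 24 h, such as delayed allergic, hepatic or haematological reactions, could still be missed.
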